All adult patients referred for a pelvic radiograph from outpatient (OP) clinics and general practitioners (GPs).

Exclusion criteria

Patients referred for one or both hip radiographs (XHIPB). Anyone with a hip prosthesis as the anatomical measures will not be valid. Immobile patients who may need additional adjustments to techniques. Patients <18 years old or pregnant. Those unable to read the participant information leaflet (PIS) or unable to provide informed written consent due to a lack of capacity (Mental Capacity Act).

Withdrawals/declining to participate

Participants may decline to participate or withdraw from the prospective study at any time without providing an explanation and without any detriment to their care. A decision to decline to consent or to withdraw will not affect the standard of care that the patient receives, as all patients will follow the diagnosis and management pathway appropriate to their clinical and radiological findings regardless of inclusion. Where patients decline to participate, no routinely collected information will be sought from NHS hospital systems about their attendance.

Study processes

Retrospective audit

The audit will be registered with each hospital site (MYH and WHTH). As the data is anonymised at source the study team will not have access to patient details thus individual consent from patients will not be sought.

The retrospective audit will be conducted for the time period of July to October 2019 to reflect the same period of the prospective study, and avoid variation in attendance numbers which may have been due to COVID-19

Prospective study:

This is a prospective interventional two arm study. One site will undertake training and then use the different technique for pelvic radiography centring (the interventional arm) and the other site will continue with usual practice. Both sites will receive feedback on the results of the retrospective audit prior to data collection via a short presentation.

Patients presenting for pelvic radiography who fit the inclusion exclusion criteria will be sent a participant information sheet (PIS) (Appendix 1) with their appointment or given one in clinic or on arrival in radiology. Posters explaining the research will also be placed in each Department's waiting area.

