Prospective data from both sites will include patient demographics (age, gender, height, and weight) and sagittal diameter at the centring point (Appendix 3). This will be recorded for each patient in the X-ray room to maintain dignity. The justification for imaging and the resultant radiograph, along with any repeats, will be collected by the research group and the resultant images will be scrutinised for axial, sagittal, and coronal rotation; image quality, and missing anatomy. This will be recorded in a password protected Excel workbook.

In the prospective cohort consented patients will undergo pelvic radiography based on the different technique or usual care, dependent upon which site they present to. The radiographer will record this, alongside the patient demographics detailed above, and justification for imaging, on a case report form (CRF – Appendix 3). The records will be anonymised and stored in a locked filing cabinet prior to analysis. The records sheet will be retained by the research team and anonymised data will be uploaded to the EDGE research management software to enable recruitment information to be collated by the NIHR portfolio and local CRN. Export of the data attributes from EDGE will be undertaken and the completely anonymised database shared with the research team for analysis. Anonymised images will be collected in DICOM format enabling analysis to be undertaken remotely. The radiation dose data will also be recorded.

Data management

Data security

The original versions of the screening logs, consent form, and CRFs will be stored in a locked filing cabinet within a locked research office at each study site. Only the research team will have access to this data. The electronic version of any data will password protected and stored on a secure drive only accessible to the direct research team. All patient identifiable information will be removed and transfer will be through encrypted devices or secure nhs.net email. All reports and dissemination of findings will only include anonymised data.

Quality control

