The research team will incorporate a rigorous programme of quality control. At regular intervals, study data will be exported from EDGE into an Excel spreadsheet and validated by a member of the research team with any data queries checked against source data. The main trial site (MYH) has an established monitoring audit programme for research studies with sponsored studies guaranteed to be appraised as part of this process, the same processes will be established at the other site (WHTH). Missing data will be recorded as an empty value.

Outcome measures

Statistical evaluation and data analysis

The data from the retrospective audit from both sites will be evaluated to determine the variability of axial, sagittal and coronal rotation; image quality, and included anatomy.

Prospective data from both sites will be analysed with descriptive and inferential statistics ICC's and Bland Altman plots (if the data is normally distributed). Data will be stratified according to Body Mass Index (BMI) in the following categories:

STOPPAGE protocol Version 1. 23.3.21 IRAS Project ID: 294098

- Underweight/Normal (BMI < 25)
- Overweight (BMI 26-30)
- Obese/morbidly obese (BMI >30)

Primary data analysis will determine the reliability of the centring point in the different technique versus usual care for sagittal, axial and coronal rotation; image quality, and included anatomy.

Secondary data analysis will compare results from within and between both sites to determine if the training and implementation of the different technique has any effect on the following:

- Obturator width left and right
- Axial pelvic rotation (degrees)
- Inter-acetabular line
- Pelvic outlet diameter
- Femoral head diameter left and right
- Inter-trochanter width
- Radiation dose
- Number of repeat radiographs
- Image quality as measured on the CRF form and from the exposure index
- Included anatomy from the iliac crests to the greater trochanters

For radiation dose data, and the number of repeats, the median and 75th percentiles will be compared.

The anonymised staff comments on the individual patient CRF's across both study arms will be descriptively analysed and a thematic analysis undertaken of any free text comments (see CRF Appendix 3).

Dose evaluation

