The data collected at both sites will include the radiation dose, measured as Dose Area Product (DAP). This will be compared to both local and national Diagnostic Reference Levels (DRL's) 2019 [34]. If any radiographs require repeating due to inadequate technical quality then these will be recorded along with the DAP. All repeat radiographs will be stored on PACS locally and transferred to the research team anonymously, no study images will be 'rejected'.

The radiographs will be undertaken with the use of Automatic Exposure Controls (AEC's) which feedback to the control panel and deliver the optimum radiation dose to the patient based on patient thickness and density (attenuation). Patient thickness will be calculated by subtracting the source object distance (SOD) from the source image distance (SID). Participant height and weight will also be recorded to allow evaluation of the effect of BMI on the subsequent radiographic technical quality.

The exposure Index (E.I.) will also be recorded for each patient. The E.I. is the measure of the amount of exposure received by the image receptor (IR). It is dependent on mAs, total detector area irradiated, and beam attenuation. The exposure index is indicative of the receptor dose, hence inherent signal to noise ratio (a measure of image quality)

Study Management

Patient and Public Involvement (PPI)

This proposal was developed with the advice and contribution of two Patient and Public Involvement (PPI) representatives from one of the study sites. The research idea was presented to the representatives and their views sought on the relevance of the research and appropriateness of the

research methods proposed. The PPI were consulted on, and approved all patient facing documents, and the group gave an opinion regarding privacy and dignity issues relating to obtaining patient size characteristics and the palpation of pelvic landmarks. Advice was incorporated and aided in a refined study proposal. PPI involvement will continue during study monitoring and when disseminating study findings. The PPI team will formally continue to the publishing of a lay summary of research findings.

Study Support

The CoRIPS grant is providing the funding. They will have no intellectual property (IP) rights to the data or outcomes arising from this study. Local CRN support will be sought help with recruitment and site file monitoring.

Dissemination

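### The exposure index part of the secondary image quality outcome measures receptor exposure, so a raw difference between the two hospitals cannot be read as a quality effect of technique

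*Protocol*

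**What the plan says.** Under Statistical evaluation and data analysis, the secondary analysis is introduced with "Secondary data analysis will compare results from within and between both sites". Its list of outcomes includes "Image quality as measured on the CRF form and from the exposure index", with radiation dose as a separate item. The sentence on the primary analysis, just above, names image quality but not EI.

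Dose evaluation defines the index: "The E.I. is the measure of the amount of exposure received by the image receptor (IR"). It adds: "It is dependent on mAs, total detector area irradiated, and beam attenuation". The reason for treating it as a quality measure is: "The exposure index is indicative of the receptor dose, hence inherent signal to noise ratio (a measure of image quality"). The same section says: "The radiographs will be undertaken with the use of Automatic Exposure Controls (AEC's) which feedback to the control panel". It also says that dose is recorded as DAP.

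On allocation, Study processes says: "One site will undertake training and then use the different technique for pelvic radiography centring (the interventional arm"); the other hospital continues with usual practice. Under Data collection, the research group also reads the prospective images directly: "the resultant images will be scrutinised for axial, sagittal, and coronal rotation; image quality, and missing anatomy".

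**The concern.** The protocol takes a quantity that it defines as exposure and enters it as a measure of image quality. This causes three difficulties.

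- **Direction.** The only link offered from EI to quality is that more receptor dose gives more signal relative to noise. No target, ceiling or acceptable range accompanies it. Read literally, more exposure is better quality, while dose is assessed separately in the same list.
- **Coverage.** EI speaks to noise alone. A rotated or clipped pelvis can have a perfectly ordinary EI.
- **Attribution.** With one hospital per arm, any difference in how the X-ray systems are set up or calibrated is inseparable from the difference in centring technique.

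At stake is the reading of one secondary result. An EI difference between the hospitals could be published as an image quality benefit, or harm, of the new centring point when it came partly or wholly from equipment.

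**Working it through.** The protocol gives no EI value, target or variability, so there is no figure of its own to reproduce here. Its one design figure, a total of 314 recruited 1:1 (Sample size), enters only as 314 / 2 = 157 per site.

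**Step 1: what an EI difference contains.** Set the protocol's statements side by side.

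- EI depends on mAs, irradiated area and attenuation (Dose evaluation).
- AEC governs the exposure according to patient thickness and density (Dose evaluation). The exposure that reaches the receptor therefore depends in part on how each system is set up. This is an inference from the use of AEC; the protocol does not say it.
- Technique and hospital coincide (Methods; Study processes).
- No common target EI, AEC matching or detector calibration between hospitals is described.

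Hence the raw difference is

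EI difference = technique (through field and attenuation) + patient mix + equipment,

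and the between-site data cannot separate the first term from the third. The planned BMI strata address part of the second term and none of the third.

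**Step 2: how an exposure offset would appear as signal-to-noise.** Assume that quantum noise dominates, so that signal-to-noise is proportional to the square root of receptor exposure, and assume identical positioning. The offsets are assumptions, not document figures.

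| Assumed exposure offset between sites | Signal-to-noise ratio between sites | Gap |
|---|---|---|
| 10% | √1.10 = 1.05 | 5% |
| 25% | √1.25 = 1.12 | 12% |
| 50% | √1.50 = 1.22 | 22% |

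The gap favours whichever hospital delivers more exposure to the receptor.

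**Step 3: how readily such an offset would reach significance.** Assume no technique effect, a pure site offset in EI, log-normal EI, 157 images per site and a two-sided 5% test. Then

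σ = √ln(1 + CV²), SE = σ √(2/157), probability ≈ Φ( ln(1 + offset)/SE − 1.96 ).

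Worked case, CV 20% and offset 10%: σ = √ln(1.04) = 0.198; SE = 0.198 × 0.1129 = 0.0224; ln(1.10) = 0.0953; 0.0953/0.0224 ≈ 4.26; Φ(4.26 − 1.96) = 0.99.

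| Offset | CV 20% | CV 30% | CV 40% |
|---|---|---|---|
| 5% | 0.59 | 0.31 | 0.20 |
| 10% | 0.99 | 0.82 | 0.59 |
| 20% | 1.00 | 1.00 | 0.99 |

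Both the CVs and the offsets are assumed. The table shows that, if the systems did differ by 10% or more, a test of raw EI at the planned sample size would probably detect the equipment. It does not show that they differ.

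**Step 4: EI and DAP.** For a given patient and field, more mAs raises both EI and DAP, so a set-up difference moves them together. Across patients under AEC this need not hold: a thicker patient needs more DAP to reach a similar receptor exposure. The two outcomes overlap for the component that matters here, but they are not the same quantity.

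**The case against.** The strongest reply has five parts.

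- **EI is only one component.** The outcome names the CRF first, and the images are read for quality separately. This stands. A reader might infer that the whole between-site image quality result measures exposure. The documents do not support that: the other two sources carry no more than the confounding by site that every between-site outcome in this design carries.
- **EI is not tied to the primary analysis.** This also stands. Because image quality appears in the primary analysis sentence, a reader might carry EI into it. The text names EI only under the secondary analysis.
- **EI can respond to technique.** Centring may change the irradiated area and the attenuation, and the protocol says that EI depends on both. So it would be wrong to say that EI reflects equipment and not technique. This stands, but a measure that mixes technique, patient and equipment is still not interpretable as quality.
- **No scoring rule says that higher is better, and reading EI against a target could be left to the analysis plan.** This stands in part. The choice of EI as a quality measure, with its receptor dose rationale, is nevertheless fixed in the protocol and is not a deferred detail.
- **A within-site comparison is planned and could remove a stable equipment offset.** It could, if EI existed for the 2019 images. The audit data listed under Data collection are rotation, image quality and missing anatomy; EI is not named.

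The complaint that EI ignores rotation and anatomy has limited force, because both are separate listed outcomes. It matters only if EI is taken to represent image quality as a whole.

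**Conclusion.** The point holds for the EI component of the secondary image quality outcome. By the protocol's own definition EI is receptor exposure and informs only on noise. With one hospital per arm and no stated harmonisation, a raw between-site difference in EI cannot be assigned to technique, and a higher value cannot be taken as better quality.

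The size is unknown. An exposure offset of 10% to 50% would give a signal-to-noise gap of 5% to 22% under the square-root law, but nothing in the documents shows that the hospitals' systems differ, or by how much. The conclusion that EI is not interpretable as quality rests on the definition and the design, not on those assumed offsets. The protocol does give a reason for its choice; the reason covers one aspect of quality.

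**What to change.** Under Statistical evaluation and data analysis, base the image quality outcome on the scored assessment of the images and on the CRF, and remove EI from that item. List EI beside DAP as an exposure indicator, expressed relative to each site's own target EI. The site's 2019 median could serve as the reference instead, but only if EI can be retrieved for the audit images. State that neither a raw between-site EI difference nor a higher EI will be interpreted as better image quality. In Dose evaluation, keep the definition of EI and describe its link to signal-to-noise as context.

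The cost is a wording change, plus obtaining each site's target EI. EI is still collected and reported, and nothing is added for patients. The small downside is that the image quality domain loses its one automatically recorded number.

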WHTH Warrington and Halton Teaching Hospitals NHS Foundation Trust

Synopsis

Study Title	St andardisation of the Su p ine P elvic R a diograph T e chnique	
Short title	STOPPAGE	
Protocol version and	Version 1.	
date	23 rd March 2021	
Study design	Multi-centre interventional study	
Study participants	Patients referred for pelvic radiography	
Planned study sample	Retrospective audit across two NHS sites (Mid Yorkshire Hospitals Trust	
	(MYH) and Warrington and Halton Teaching Hospitals NHS Foundation Trust	
	(WHTH) of existing pelvic radiographs obtained in the same time period in	
	2019 (June to October).	
	Prospective convenience sample of patients attending either of the two NHS	
	hospitals for supine pelvic radiography. The target sample size is n=314	
	across two NHS sites. Recruitment will be on a 1:1 basis	
Planned study period	Recruitment July to October 2021.	
	Data analysis, write up and dissemination November 2021 to March 2022	
Primary objective	To standardise the acquisition of supine pelvic radiographs and determine	
	the reliability of a different evidence based centring point with respect to	
	sagittal axial and coronal rotation, image quality, and included anatomy.	
Secondary objectives	To assess if the different centring point reduces the number of repeat	
	radiographs required due to unacceptable technical quality	
	To determine the average radiation dose of the different centring point	
	compared with 'usual practice'	
	To determine the perceptions of locating bony landmarks for both	
	techniques amongst radiographers	
Underlying hypothesis	The different centring point will reduce variability in pelvic radiograph	
	measurements and be more acceptable to radiographers than the current	
	standard of positioning	

Summary

Radiographic projections should be standardised to enable consistent and accurate interpretation and measurements, but textbooks and clinical practice describe various methods.

This variation can lead to problems with measurements which determine patient outcomes, and this is particularly evident within pelvic radiography. This has implications for orthopaedic surgeons who need accurate measurements to plan hip replacements and assess the joints. In some instances, radiographers 'centre low' to demonstrate the hips, whereas others include iliac crests as a true 'pelvis'.

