The different centring point being evaluated at the interventional site is based on features of the key anatomy being studied (the hips) and could be relevant regardless of patient body habitus, anatomical variation (pelvic tilt) and orientation (supine or standing). There is a clear gap in knowledge as to whether centring derived from different surface anatomy reference points result in the same image, radiation dose, and diagnostic quality and there is a need for greater standardisation in clinical practice and a robust underpinning evidence base.

The aim of this study is to provide evidence for a different centring point that has been developed from a previous image review study [1, 33] and determine its reliability and acceptability to radiographers. Providing evidence for optimum position is the first step to ensure radiography is evidence based and allows future development of an evidence base for other body parts. In addition, it provides a platform from which to consider changes to technique, such as the increasing requirement for weight-bearing images.

Principal aim of the study

To validate a different centring point for pelvic radiographs in a supine position.

Primary research question

What is the variability between the different pelvic centring point in a range of patient body habitus?

Secondary research questions

- Does the different centring point undertaken at the interventional site lower the number of X-ray repeats when compared to usual practice undertaken at the control site?
- What is the variability in pelvic radiographs (i.e. rotation and inclusion of anatomy) with the different method versus 'usual practice'?
- What is the average radiation dose for the different centring point compared to usual practice?
- What are the perceptions of radiographers in the ease of using the different centring point?

Methods

This study will test the different centring point for reliability and acceptability. Two NHS clinical sites in England will be used with one undertaking pelvis radiography according to the different technique (intervention site) and the other continuing with standard practice (control site).

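### The dose comparison rests on medians and 75th percentiles from two non-randomised sites; the general BMI stratification is not tied to it and would leave some confounding by body size

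*Protocol*

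**What the plan says.** The Protocol's secondary research questions ask: "What is the average radiation dose for the different centring point compared to usual practice". Under Dose evaluation, "The data collected at both sites will include the radiation dose, measured as Dose Area Product (DAP"). Radiation dose is one of the secondary outcomes listed under Statistical evaluation and data analysis, and the one sentence there on how to compare it reads "For radiation dose data, and the number of repeats, the median and 75th percentiles will be compared".

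The groups are not randomised. The Synopsis describes a "Prospective convenience sample of patients attending either of the two NHS" hospitals, and Data collection says that patients have the different technique or usual care "dependent upon which site they present to".

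Dose evaluation says that the automatic exposure controls (AEC) "deliver the optimum radiation dose to the patient based on patient thickness and density (attenuation"). It then says how thickness will be calculated from two source distances, and adds: "Participant height and weight will also be recorded to allow evaluation of the effect of BMI on the subsequent radiographic technical quality". Data collection has height, weight and the sagittal diameter at the centring point recorded for each prospective patient.

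Statistical evaluation and data analysis also says, in general terms, that data will be stratified into three BMI bands: below 25, 26 to 30, and "Obese/morbidly obese (BMI >30"). It neither names dose nor excludes it.

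**The concern.** The protocol names body size as what the exposure control responds to and measures it in every patient, but its dose sentence does not use it. Nothing in the design balances body size between the hospitals. If one hospital's patients are larger on average, its dose will be higher whichever centring point is used. The difference could be reported as an effect of the technique, or could hide one.

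No baseline is described that would reveal this. The retrospective audit lists rotation, image quality and anatomy, but not dose. The stated purpose of height and weight is technical quality rather than dose.

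At stake is the answer to a stated secondary objective. The primary analysis is not affected.

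**Working it through.** The protocol gives no figure for the dose comparison (no expected dose, spread or detectable difference), so there is nothing to reproduce. The check asks how much body-size imbalance passes into the stated comparison, and how much the BMI bands would remove.

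**Inputs from the protocol.** 314 patients recruited 1:1, so 314 / 2 = 157 per site; one technique per site; three BMI bands.

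**Assumed inputs (not in the documents).** BMI normal with mean 28 and SD 5; log dose-area product (DAP) linear in BMI with slope β = 0.03, 0.05 or 0.08 per unit (about 3%, 5% or 8% per unit); residual SD of log DAP 0.4; difference Δ in mean BMI between sites of 1, 2 or 3 units; no technique effect.

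**Step 1: no stratification.** Under this model the median ratio and the 75th-percentile ratio both equal exp(β × Δ):

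| Δ (BMI units) | β = 0.03 | β = 0.05 | β = 0.08 |
|---|---|---|---|
| 1 | 1.03 | 1.05 | 1.08 |
| 2 | 1.06 | 1.11 | 1.17 |
| 3 | 1.09 | 1.16 | 1.27 |

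Simulation (1,000 repetitions per scenario) agrees: 1.03 to 1.27 for both the median and the 75th percentile.

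**Step 2: false-positive rates at a nominal 5%.** The protocol names no test for dose, so the unstratified comparison used a Mann-Whitney test. The other two used linear regression of log DAP on site, with BMI in three classes or continuous.

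| Δ | No stratification | Three BMI classes | Continuous BMI |
|---|---|---|---|
| 1 | 9 to 24% | 5 to 7% | 5% |
| 2 | 22 to 68% | 5 to 11% | 5 to 6% |
| 3 | 42 to 95% | 8 to 18% | 4 to 6% |

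With three classes the null ratio is 1.01 to 1.05. In the worst case, ln(1.053) / ln(1.268) = 0.052 / 0.237 = 0.22, so the bands remove a little under four fifths of the bias on the log scale. This favours the bands in two ways: the simulated classes were cut at 25 and 30 with no gap, and they were combined in one model, which the protocol does not say it will do. The continuous-BMI rates stay near 5% partly because the data were generated linear in BMI.

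**Step 3: the bands as written.** The first band ends below 25 and the second starts at 26, so a BMI from 25 up to 26 has no band. If BMI is normal with mean 27 to 29 and SD 4 to 6 (assumed), that holds about 5.6% to 9.3% of patients: 0.056 × 314 ≈ 18 to 0.093 × 314 ≈ 29 people.

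**Step 4: what a stratified comparison would yield.** Two percentiles in each of three bands give three pairs of site comparisons and no rule for combining them. With 157 per site, an even split gives 157 / 3 ≈ 52 patients per cell, and fewer in the smaller cells if the split is uneven.

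**The case against.** A reader might infer that dose will be compared wholly unadjusted. The documents do not support that. The BMI stratification stands in the same section, before the dose sentence, and can fairly be read to cover every prospective outcome. On that reading most of the imbalance is dealt with, and bands against continuous BMI becomes a matter of degree. This part of the objection stands, and the point is framed accordingly.

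A reader might also infer that the 75th percentile is governed by the open-ended top band. That can apply only to a pooled percentile; with strata, each band has its own.

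Nor do the documents show that the hospitals differ in body size. Both recruit adult outpatient and GP referrals under the same criteria. The inputs to the calculation are assumed, and Dose evaluation does provide for measuring thickness. All of this is correct, so the size is illustrative.

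Finally, a statistical analysis plan that is not shown could specify a model. But the point does not rest on missing detail. The protocol does state a dose method, and percentiles compared between self-selected sites are a poor choice when the main known driver of dose is recorded. Reading the strata into it still gives no single answer to the secondary question, leaves some patients in no band, and keeps confounding within bands.

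**Conclusion.** The point holds in a limited form. The stated dose method is weak for a non-randomised comparison. The BMI bands, if they apply to dose, would remove most but not all of the confounding by body size. On the assumed inputs, site differences of 1 to 3 BMI units with no technique effect give a median ratio of about 1.03 to 1.27 without stratification and about 1.01 to 1.05 with three classes. The corresponding false-positive rates are 9 to 95% and about 5 to 18%, against about 4 to 6% with continuous BMI. These figures depend on the assumed BMI distribution, slope and residual spread. They show the direction and rough scale of the problem and do not predict the bias in this trial.

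A reader might infer that body-size adjustment would isolate the effect of the centring point. It would not. Each technique is used at one site only, so equipment, AEC settings and staff remain mixed with it.

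Because dose is a secondary objective and the remedy uses data already collected, the change should be made, but nothing else in the study hangs on it.

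**What to change.** - Make the between-site dose comparison a linear regression of log DAP on site/technique, with continuous weight and height (or BMI) as covariates. Report the adjusted DAP ratio with a 95% interval.
- Keep medians and 75th percentiles, overall and by BMI band, as descriptive figures and for the comparison with diagnostic reference levels. Make the bands contiguous so that every patient falls in one.
- Do not use the sagittal diameter taken at the centring point as the covariate. That point differs by technique, so the measurement may itself be changed by the intervention, and adjusting for it could remove part of the effect or add bias. The thickness derived from the source distances needs the same caution if it is taken at the centring point.
- State in the protocol and the report that the adjusted ratio combines technique with site (equipment, AEC settings, staff).

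The cost is a few sentences of analysis wording and one regression on data already planned for collection. No extra patients or measurements are needed.
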